# Date: 15 August 2019 EudraCT No.: 2018-002945-12

Sponsor: ACO Hud Nordic AB

Study Code: Novum ACO-CT-2018-01

#### **6 STUDY OBJECTIVES**

#### 6.1 Primary Objective

The primary objective is to determine whether applying a new moisturizing cream (the test cream) for 4 weeks is superior in terms of skin barrier strengthening, when compared with (1) no treatment and (2) two reference creams in adults with a predisposition to a skin barrier defect.

- TEWL after induction of skin irritation
- Redness after induction of skin irritation

The hypotheses for the study are provided below in order of importance:

- a) Skin irritation, indicated by elevated TEWL and redness, will be reduced following treatment with the test cream compared to the untreated control.
- b) Skin irritation, indicated by elevated TEWL and redness, will be reduced following treatment with the test cream compared to the reference creams, Miniderm 20% cream and Diprobase cream.

#### 6.2 Secondary Objectives

Secondary objectives: To determine whether there is a difference between the new moisturising cream (the test cream) and (1) no treatment and (2) the two reference creams in:

- Resting skin barrier function
- Skin moisturisation
- Tolerability
- Cream consumption
- Safety

Confidential Page 19 of 65

Sponsor: ACO Hud Nordic AB Study Code: Novum ACO-CT-2018-01 EudraCT No.: 2018-002945-12

#### 7 STUDY DESIGN

[figure not shown]
#### 7.1 Study Design and Plan-Description

A prospective phase 2 within-subject multilateral randomised controlled trial to determine the superiority of the test treatment at strengthening the skin barrier compared to no treatment and two reference treatments in adults with a predisposition to a skin barrier defect.

Participants will treat their lower volar forearms for 28 days with three different creams (Miniderm Novum (test cream), Miniderm 20% cream or Diprobase cream) and leave one area untreated as a control. Each forearm will have two different treatment areas and treatment allocation will be randomized (right arm upper, right arm lower, left arm upper, left arm lower). One Finger Tip Unit (FTU) of each cream will be applied twice daily on the designated study area. As such there will be four treatment conditions (with each participant undertaking all 4 treatment conditions):

- 1. No treatment (control),
- 2. Miniderm Novum (test cream),
- 3. Miniderm 20% cream or
- 4. Diprobase cream

#### Study overview:

The participants will record details of cream application frequency, as well as participant tolerability in a diary. At each study visit, concomitant medication and any AEs are noted in the Case Report Form (CRF). The study medication will be collected and weighed in order to estimate cream consumption.

Participants will attend 5 clinic visits during the study:

- Visit 1 (screening) will be performed at baseline
- Visit 2 will be performed after 5 days of treatment

Confidential Page 20 of 65

Version: Version 3.0 Date: 15 August 2019 Sponsor: ACO Hud Nordic AB Study Code: Novum ACO-CT-2018-01 EudraCT No.: 2018-002945-12

- Visit 3 will be performed after 15 days of treatment
- Visit 4 will be performed after 29 days of treatment
- Visit 5 will be performed 1 day after SLS-patch removal (Day 31 after start of treatment)

The study design is visualised in Figure 2.

Figure 2 Overall Study Design

Confidential Page 21 of 65

Version: Version 3.0 Date: 15 August 2019 Sponsor: ACO Hud Nordic AB
Study Code: Novum ACO-CT-2018-01

EudraCT No.: 2018-002945-12

#### 7.3 Recruitment Period

The expected recruitment period is 3 months. This is calculated to be sufficient to include 50 participants with a mean accrual rate of 3.3 participants per week.

#### 7.4 Study Period

First participant first visit is expected to be in February 2019.

Last participant last visit is expected to be in April 2019.

#### 7.5 End of Study

The end of study is defined as the date of the last participant's last visit.

Confidential Page 22 of 65

Version: Version 3.0 Date: 15 August 2019 Sponsor: ACO Hud Nordic AB Study Code: Novum ACO-CT-2018-01 EudraCT No.: 2018-002945-12

#### **8 INVESTIGATIONAL PLAN**

#### 8.1.1 Schedule of events

The schedule of events for the study is shown in **Error! Reference source not found.**.

Confidential Page 23 of 65

Version: Version 3.0 Date: 15 August 2019 Sponsor: ACO Hud Nordic AB Study Code: Novum ACO-CT-2018-01 EudraCT No.: 2018-002945-12

Table 2 Schedule of events

	Screening	Visit 1 Baseline a,b	Visit 2 5 days b (+/- 2 days)	Visit 3 15 days b (+/- 3 days)	Visit 4 29 days b (+/- 3 days)	30 days c (+/-3 days)	Visit 5 31 days b (+/-3 days)
Screening & Enrolment:							
Informed consent	X						
Confirm eligibility	X						
Demographic data	Х						
Medical history	X						
Screening (& admission)	X						
Randomisation		X			Х		
Reconfirm ascent		Х	Х	Х	Х		Х
Concomitant medication	X	Х	Х	Х	Х		Х
Adverse events	Х	Х	Х	Х	Х		Х
Skin assessments:							
Acclimatize test sites		Х			Х		Х
TEWL measurement		Х			Х		Xd
Capacitance measurement		Х			Х		
Image skin (2D – colour)		Х		Х	Х		Xd
Objective redness					V		Xq
measurement					Х		^-
Visual grading of redness					Х		Xd
Image skin (3D - roughness)		X			Х		
Saliva sample collection		Х					
NMF sample collection					Х		
SLS application					Х		
SLS removal						Х	
Measurement of SLS- exposed skin (TEWL and redness d )							Xd
Treatment:							
Dispensation of investigative products and participant diary		Х					
Instructions to participants		Х					
Supervised product application		Х	Х	X	×		
Review of participant diary and weigh treatments		Х	Х	Х	Х		
Collection of participant diary					Х		
Collection of investigational products					Х		

<sup>a The screening and baseline visit may be combined providing sufficient time is given to allow parents to properly consider the study.

#### 8.1.2 Recruitment

Recruitment will be conducted in several ways:

Confidential Page 24 of 65

b Face-to-face meeting

<sup>c Participants removes SLS-patch after 24 hours and rinses with lukewarm water.

d Measurement of skin irritation only

Version: Version 3.0 Date: 15 August 2019 Sponsor: ACO Hud Nordic AB Study Code: Novum ACO-CT-2018-01 EudraCT No.: 2018-002945-12

General advertisement using posters (see attached PosterAdvert and AltMediaAdvert).
 The poster contains telephone and email contact details for the study team. Posters (see attached) will be displayed at:

- a. The University of Sheffield premises, including the Medical School
- b. Sheffield Hallam University (SHU) premises, with permission
- c. Online, on the University of Sheffield website, SHU website (student portal), Facebook, Twitter, including @Shef Derm Twitter pages
- 2. Email lists. An email, containing the information in the \*Advert (and a copy of the Participant Information sheet, PIS), will be distributed to:
  - an email list of people who have either expressed an interest in or have taken part in our research projects previously (where consent has been provided to do this)
  - b. staff and students at the University of Sheffield, and SHU using the appropriate moderated email lists at each institution.

The study office will handle all expressions of interest. Participants responding to our adverts/letters by phone/email will be asked to complete a registration form/expression of interest form (this may be done by phone/email/post).

#### 8.1.3 Informed Consent

People responding to study advertisements will be provided with a Participant Information Sheet (PIS) and a study Registration Form.

A member of the study team will then contact interested volunteers to arrange a screening visit at the test centre. While it is preferable to conduct the screening visit in person, it can be conducted by telephone at the participants request.

A screening number will be assigned using the SDR Subject Screening Log at the point of first contact to record approaches.

At the start of the screening visit (at least 24 hours after provision of the PIS), a study researcher (as delegated by the PI), trained in informed consent taking, will conduct the informed consent process. All participants will be provided with a Consent Form to sign, of which they will be provided a copy to keep.

Following Informed Consent, we will complete the study Registration Form (if not already complete), the Background Information Form (includes medical history), together with the NESS Body Map form, and determine whether the participant meets the inclusion/exclusion criteria detailed on the Admission Form.

Upon successful screening, all study appointments will be arranged such that participants have undergone a 1-week wash-out period for any topical products (excludes wash products) they may use on the skin of their test sites.

Confidential Page 25 of 65

Version: Version 3.0 Date: 15 August 2019 Sponsor: ACO Hud Nordic AB Study Code: Novum ACO-CT-2018-01 EudraCT No.: 2018-002945-12

A screening number will be assigned using the Screening, Enrolment and Completion Log at the point of first contact to record approaches.

The Enrolment Log will be completed and all enrolled participants assigned a unique study ID.

**Note for remote screening sessions:** Where the screening is conducted by telephone the participants will be notified of the inclusion and exclusion criteria and asked to confirm whether they think they meet the criteria or not without further discussion or collection of the participants medical history. This will help minimise the number of volunteers who are invited to the test site who are then found to be unsuitable upon completion of screening, whilst also protecting the participants privacy. Under these circumstances Consent, Screening, and completion of the Background Information Form will need to be undertaken at the start of Visit 1.

#### 8.1.4 Study Visits

The study assessments described in the sections below are presented in detail in Section 11.2 (efficacy assessments), Section 11.3 (demographic data and baseline characteristics) and Section 11.4 (safety assessments). Recording and reporting of AEs are described in detail in Section 12.

The timing of all study events is shown in Error! Reference source not found. in Section 8.1.1.

#### 8.1.4.1 Visit 1 (Screening and baseline)

Before any study specific procedures are performed, the participants will sign the informed consent form. After written informed consent has been obtained, the following assessments and activities will be performed:

- History of AD will be diagnosed according to UK working party criteria (37) (see also Section 9.2)
  - According to the UK working party diagnostic criteria (37), eczema is defined as exhibiting an itchy skin condition in the past 12 months plus 3 or more of:
    - History of involvement of the skin creases
    - Personal history of asthma or hay fever
    - History of generally dry skin in past year
    - Visible flexural dermatitis
    - Onset below age 2
- Demographic data and baseline characteristics will be recorded (sex, date of birth, race)
- Medical history will be recorded
- Prior (see section 8.3 for details) and concomitant medication will be recorded
- Inclusion and exclusion criteria will be evaluated
- Eligible participants will be given a participant number

Confidential Page 26 of 65

Version: Version 3.0 Date: 15 August 2019 Sponsor: ACO Hud Nordic AB Study Code: Novum ACO-CT-2018-01

EudraCT No.: 2018-002945-12

- Participant randomization
- AE recording will start
- The test sites will be acclimatized to the room conditions for ≥20 minutes
- Baseline measurements will be performed
  - Measurement of Trans Epidermal Water Loss (TEWL)
  - Measurement of skin capacitance
  - 3D skin images captured (roughness evaluation)
  - 2D skin images captured (colour evaluation)
- Collect a saliva sample for genotyping
- Study creams (weighed) will be dispensed
- Diary will be handed out (for recording cream application and tolerability)
- The researcher will provide instructions to the participant
- The participant will be asked to perform the first treatment applications under supervision
- The first patient-orientated skin tolerability assessment will be recorded in the diary buy the participant

The participants will start applying the creams on the same day as Visit 1 is performed.

Before leaving the clinic, the participants will be informed about the restriction criteria and they will be instructed to return to the clinic 29 days (±3 days) later for measurement of TEWL and skin capacitance. The participant will also be instructed how to fill out the diary and to bring the investigational products to the last visit.

#### 8.1.4.2 Visit 2 (Review of participant diary and weigh treatments, Day 5 (±3 days))

At Visit 2, the following assessments and activities will be performed:

- Review of participant diary
- Weigh test and reference products
- AEs recorded
- Concomitant medications will be recorded
- Remind the participant to complete the second patient-orientated skin tolerability assessment in the diary

#### 8.1.4.3 Visit 3 (Review of participant diary and weigh treatments, skin image, Day 15 (±3) days))

At Visit 3, the following assessments and activities will be performed:

Review of participant diary

Confidential Page 27 of 65

Version: Version 3.0 Date: 15 August 2019 Sponsor: ACO Hud Nordic AB Study Code: Novum ACO-CT-2018-01 EudraCT No.: 2018-002945-12

- Weigh test and reference products
- Image analysis of the skin
- AEs recorded
- Concomitant medications will be recorded
- 2D skin images captured (colour evaluation)

#### 8.1.4.4 Visit 4 (Evaluation of TEWL change, start of SLS exposure, Day 29 (±3 days))

At Visit 4, the following assessments and activities will be performed:

- Diary will be collected and reviewed
- Ensure the participant has completed the third patient-orientated skin tolerability assessment in the diary
- Collect and weigh test and reference products
- Concomitant medications will be recorded
- AEs recorded
- Restriction criteria will be evaluated
- The test sites will be acclimatized to the room conditions for ≥20 minutes
- Skin measurements will be performed
  - Measurement of Trans Epidermal Water Loss (TEWL)
  - Measurement of skin capacitance
  - o 3D skin images captured (roughness evaluation)
  - 2D skin images captured (colour evaluation)
  - Objective skin redness will be measured using the Mexameter
  - Visual scoring of redness
- Collect NMF samples
- SLS application
- The researcher will provide instructions to the participant

#### 8.1.4.5 Visit 5 (Evaluation of TEWL change, Day 31 (±3 days))

At Day 30, the SLS-patch will be removed by the participant at home and the skin will be left to recover for 24 h.

At Visit 5, the following assessments and activities will be performed:

- Concomitant medications will be recorded
- Restriction criteria will be evaluated

Confidential Page 28 of 65

Version: Version 3.0
Date: 15 August 2019

Sponsor: ACO Hud Nordic AB Study Code: Novum ACO-CT-2018-01 EudraCT No.: 2018-002945-12

• The test sites will be acclimatized to the room conditions for ≥20 minutes

- Skin measurements will be performed
  - Measurement of Trans Epidermal Water Loss (TEWL)
  - o 2D skin images captured (colour evaluation)
  - o Objective skin redness will be measured using the Mexameter
  - Visual scoring of redness
- AEs recorded

Confidential Page 29 of 65

Version: Version 3.0 Date: 15 August 2019

## 8.2 Collection of human samples

The following types of human tissue/biological material will be collected as part of this study:

1. Stratum corneum samples for quantification of Natural Moisturising Factor (NMF) levels

Sponsor: ACO Hud Nordic AB

EudraCT No.: 2018-002945-12

Study Code: Novum ACO-CT-2018-01

2. Saliva Samples to obtain genomic DNA for the determination of FLG gene status.

The samples will be stored in linked-anonymised form, meaning that they will be labelled with a participant ID and participant initials for identification (and not personal identifiable information, PII). The link between the participant ID and PII will be kept in the site file and only be accessible to the direct study team.

The samples will be stored at the test site under the custodianship of the PI. All samples, except the extracted DNA, will be destroyed within 1 year following the last participants last visit. Extracted genomic DNA will be kept under the custodianship of the PI for use in future research project, unless specific consent for this is not obtained (separately specified on the ICF).

#### 8.2.1 Stratum corneum samples

Superficial skin samples are collected by tape stripping. Tape stripping is a painless procedure that removes the dead cells (denucleated corneocytes) from the surface of the skin that will eventually be lost/shed as a result of normal desquamation. It can cause some discomfort and redness, but any redness usually dissipates in a matter of hours/days. No dressings are required. The only skin preparation required before tape stripping is the removal of visible contaminants by dry wipe if necessary.

The samples collected by tape-stripping described herein do not meet the definition of relevant material under the Human Tissue Act because they contain no viable human cells (corneocytes are non-viable terminally differentiated/dead cells).

#### 8.2.2 Saliva Samples

A saliva sample will be collected from the inside of the participants cheek during visit 1 in order to obtain a sample of genomic DNA. It can be easily collected by the participant themselves. Extracted genomic DNA will be genotyped for the 5 most common *FLG* gene mutations. The filaggrin gene (*FLG*) encodes proteins that are key to the normal barrier function of the skin. Null mutations in *FLG* are associated with an increased risk of eczema. Understanding how these mutations affect the responses to topical treatment is therefore of interest.

Confidential Page 30 of 65

Version: Version 3.0 Date: 15 August 2019

#### 9 SELECTION OF STUDY POPULATION

#### 9.1 Number of Participants

It is estimated that 50 evaluable participants will be needed (see Section 13.2 for sample size calculation).

Sponsor: ACO Hud Nordic AB

EudraCT No.: 2018-002945-12

Study Code: Novum ACO-CT-2018-01

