#### NUMBER OF PARTICIPANTS and statistical evaluation:

50 participants will be recruited into the study. This sample size is sufficient to provide more than 90% power to detect a difference (test treatment vs no treatment) of 3.5 in change in TEWL for the primary endpoint, if the data is suitable for a parametric analysis. If the observed data is not suitable for a parametric analysis then the sample size would provide greater than 80% power in a non parametric analysis.

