## 13.2 Determination of Sample Size

The sample size for this study is based on the primary end point, change in TEWL after induction of skin irritation (change between day 19 and day 21), with the primary comparison being between the test treatment and no treatment and the secondary comparison being between the test treatment and the two reference treatments.

In a similar study the standard deviation of the difference in change in TEWL after induction of skin irritation was seen to be approximately 8 g/m²/h when comparing the no treatment group to an active treatment. (that is: standard deviation of {[Change after skin irritation in no treatment area]-[Change after skin irritation in active treatment area]}).

When comparing the difference between the test treatment and one of the two reference treatments the standard deviation was approximately 3.

If the assumptions of a paired t-test are found to be valid, for a sample of 40 participants this analysis would have >90% power to detect a difference (in change) of 3.5 g/mÇ.h between test treatment and no treatment. The same sample size would also have >90% power to detect a difference (in change) of 2 g/mÇ.h between test treatment and active treatment. If a parametric analysis is indicated then an analysis which includes the baseline as a covariate will be considered which, if there is variation at baseline may increase the power of the analysis further.

If the assumptions of a paired t-test are not met (and a suitable transformation cannot be found) then a sign test (or a wilcoxon matched pairs test) may be used. A power calculation can be carried out for the sign test (46) although this too makes some assumptions. This calculation shows that a sample size of N=40 would have >80% power to detect a difference such that the probability of X>0 (where X is the difference in change, as above) is approximately 0.7. This probability is not unrealistic given the data seen previously, and, if the clinically relevant difference detailed above is seen, the probability of X>0 may in fact be increased leading to higher power. To account for dropouts, 50 subjects will be recruited.

Confidential Page 55 of 65

Version: Version 3.0 Date: 15 August 2019 Sponsor: ACO Hud Nordic AB Study Code: Novum ACO-CT-2018-01 EudraCT No.: 2018-002945-12

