# 2. Study Methods

# 2.1 Study Design

It is planned to recruit 40 adults (male and female, aged 18 and above) with personal history of atopic dermatitis but no current eczema on the volar forearms and no possible allergy to the ingredients in the study medications.

Four treatment sites on the lower volar forearms (two on the right and two on the left) will be randomised for each participant with one treatment to be applied to each of three sites and the fourth remaining untreated as a control. The four treatment groups are;

- No treatment (control)
- Miniderm Novum (test cream)
- Miniderm 20% (reference cream)
- Diprobase (reference cream)

One Finger Tip Unit (FTU) of each cream will be applied twice daily on the designated study area. The participants will record details of cream application frequency, as well as participant tolerability in a diary.

Subjects will remain in the study for 4-5 weeks.

At each study visit, concomitant medication and any AEs are noted in the Case Report Form (CRF). The study medication will be collected and weighed in order to estimate cream consumption.

Participants will attend 5 clinic visits during the study:

- Visit 1 (screening) will be performed at baseline (Day 1)
- Visit 2 will be performed after 5 days of treatment
- Visit 3 will be performed after 15 days of treatment

- Visit 4 will be performed after 29 days of treatment
- Visit 5 will be performed 1 day after SLS-patch removal (Day 31)

Assessors will be blind to the treatment assigned to each site. Subjects will be blinded to the cream assigned to each study site – although the untreated site will remain unblinded.

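### The number of participants is stated three ways (50 evaluable, 50 recruited, 40 recruited), and the SAP's version drops the drop-out allowance without declaring it

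*Protocol*

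**What the plan says.** The current texts give these figures:

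- **Protocol 9.1:** "It is estimated that 50 evaluable participants will be needed", with a reference to Section 13.2.
- **Protocol 13.2:** "for a sample of 40 participants this analysis would have >90% power to detect a difference (in change) of 3.5" g/m²/h between test cream and no treatment. The section ends: "To account for dropouts, 50 subjects will be recruited".
- **Protocol synopsis:** "50 participants will be recruited into the study". It attaches the power above 90% to this 50, where 13.2 attaches it to 40.
- **Protocol 7.3:** an expected recruitment period of 3 months, with the remark "This is calculated to be sufficient to include 50 participants with a mean accrual rate of 3.3 participants per week".
- **SAP 2.1:** "It is planned to recruit 40 adults".
- **SAP 2.3:** repeats the Protocol's calculation for 40 but stops before the sentence on drop-outs and 50 recruits.
- **SAP 7.9:** lists one change from protocol, an exploratory look at the location and adherence of the SLS patches.

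Neither document states a drop-out rate or says whether a withdrawn participant is replaced. Protocol 9.6 covers only the use of data collected up to withdrawal. Protocol 13.1.2 and SAP 7.6 say that missing data are not replaced.

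**The concern.** Section 9.1 contradicts the section it cites. If 50 is the number recruited, with losses expected, then 50 is not the number evaluable. The word evaluable also matches no analysis set: the FAS is everyone randomised with a history of AD, whether or not a Day 31 value exists, and neither the PPS nor the Safety set is defined by having one.

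The SAP's 40 looks like more than a slip in one place, because SAP 2.3 also lacks the sentence that turns 40 into 50. Read together, SAP 2.1 and 2.3 recruit exactly the number on which power was calculated and allow for no losses.

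This affects precision. The primary TEWL outcome is the change from Day 29 to Day 31, and missing values are not replaced, so the number of participants with both readings determines the power of the comparison with no treatment.

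**Working it through.** **Inputs**

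- Difference of 3.5 for test versus no treatment, and a calculation at N = 40 (Protocol 13.2).
- SD for that contrast: "the standard deviation of the difference in change in TEWL after induction of skin irritation was seen to be approximately 8" g/m²/h.
- Test versus reference: difference of 2, and "When comparing the difference between the test treatment and one of the two reference treatments the standard deviation was approximately 3".
- Two-sided 5% level (SAP 7.5). The sample-size text does not state sidedness.
- Drop-out rate: not in the documents. Assumed range 5% to 20%. The upper end is the rate at which 50 recruits leave 40, since 40/50 = 0.80.

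**Step 1. Reproduce the plan's power.** For a paired t-test the noncentrality is difference / (SD/√N).

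- Test versus no treatment, N = 40: 3.5 / (8/√40) = 2.77. Power is 77.0% two-sided (79.0% by the normal approximation) and 85.9% one-sided. The stated figure above 90% is not reproduced.
- Same contrast, N = 50: 3.5 / (8/√50) = 3.09. Power is 85.8% two-sided and 92.0% one-sided.
- 90% power needs 57 with both readings two-sided, or 47 one-sided.
- Test versus reference, N = 40: 2 / (3/√40) = 4.22. Power is 98.4% two-sided, so this claim is reproduced.

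**Step 2. Compare the three statements.** Completers = recruited × (1 − d). Recruits needed for 50 evaluable = 50 / (1 − d), rounded up. Completers are rounded down. Power is two-sided for 3.5 with SD 8.

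| Assumed drop-out d | SAP 2.1: recruit 40 | Protocol 13.2: recruit 50 | Protocol 9.1: 50 evaluable |
|---|---|---|---|
| 5% | 38 complete, power 74.7% | 47 complete | recruit 53 |
| 10% | 36 complete, power 72.3% | 45 complete, power 81.9% | recruit 56 |
| 15% | 34 complete, power 69.7% | 42 complete | recruit 59 |
| 20% | 32 complete, power 66.9% | 40 complete, power 77.0% | recruit 63 |

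At 20%, planned enrolment runs from 40 to 63 depending on the section read.

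**Step 3. Recruitment period.** 50 / 3.3 = 15.2 weeks. Three months is about 13 weeks, and 13 × 3.3 = 42.9, or about 43 participants. The period, the rate and the target of 50 do not agree.

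**The case against.** The strongest reply is that the site works from the Protocol, which gives 50 as the number recruited or included in three places: the synopsis, 7.3 and 13.2. Section 9.1 is worded as an estimate and sends the reader to 13.2. The SAP's 40 stands in a descriptive design section and triggers nothing: SAP 2.4 starts the analysis once all participants have finished or discontinued, and the FAS takes everyone randomised with a history of AD. This stands. A reader might infer that the site cannot tell when to stop recruiting, but the documents do not support that. What remains for the site is narrower: 50 enrolled or 50 evaluable, with no word on replacement.

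Three other inferences also go too far:

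- **That the plan assumes 20% drop-out.** It states no rate. The 20% comes only from dividing 40 by 50, which is why a range is shown.
- **That the trial will end short at the stated accrual.** Section 7.3 gives an expected period, not a stopping rule, and the same passage aims for 50. Even if recruitment stopped at 43, completers would fall below 40 only if drop-out exceeded about 7% (1 − 40/43).
- **That recruitment could be adjusted in a way that biases the result.** No interim analysis is planned, and the statistician receives the unblinding information only at database lock.

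The plan can also say that a baseline covariate may raise power. It gives no figure for the gain. By the normal approximation, 90% two-sided power at 40 would need an SD of about 6.8 rather than 8.

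**Conclusion.** The point holds as an inconsistency in the current text of both documents. Protocol 9.1 conflicts with 13.2, the synopsis and 7.3. SAP 2.1 and 2.3 conflict with the Protocol, remove its drop-out allowance, and do not declare the change.

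Over 5% to 20% drop-out, following the SAP's number would leave 38 to 32 completers rather than about 47 to 40. For the comparison with no treatment, two-sided power would be 74.7% to 66.9%. These figures rest on the plan's own difference and SD, a paired t-test, a two-sided 5% level and an assumed drop-out range. The contradiction itself does not depend on the drop-out rate.

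A reader might infer from 13.2 that 40 completers are enough and that only the wording needs aligning. The plan's own inputs do not support this: power is 77.0% at 40 and 85.8% at 50, against a stated value above 90%. The comparison with the reference creams is not affected in this way; its power is still 95.5% at 32 completers. The accrual mismatch is minor and concerns the schedule only.

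**What to change.** 1. **SAP 2.1:** change 40 to 50 recruited. **SAP 2.3:** restore the Protocol's sentence on drop-outs and 50 recruits.
2. **Protocol 9.1:** replace 50 evaluable with 50 recruited. Give the assumed drop-out rate and the number expected to have both Day 29 and Day 31 TEWL.
3. **Replacement:** the sponsor should state whether withdrawn participants are replaced. The documents support neither answer, so this is the sponsor's decision.
4. **Power:** in the synopsis, Protocol 13.2 and SAP 2.3, restate power for test versus no treatment at the expected number of completers, with sidedness given. Two-sided it is 77.0% at 40 and 85.8% at 50. Do not describe 40 completers as giving more than 90%.
5. **Protocol 7.3 (minor):** give about 15 weeks at 3.3 per week, or about 3.8 per week for 13 weeks (50/13 = 3.8).

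The cost is wording in both documents and one recalculated power statement. Keeping 50 recruited adds no participants. Extra recruitment would arise only if the sponsor chose to replace withdrawals or to hold to 90% two-sided power, which needs 57 with both readings.
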